3. CHARACTERISTICS OF THE RESEARCH POPULATION

3.1. Subject Characteristics

a) Number of Subjects:

Target accrual is 30 evaluable CLL or WM subjects receiving treatment with BTK inhibitors. Assuming a 10% drop out rate, we aim to enroll a total of 33 subjects. Participants will be replaced in case of drop out or failure to receive the second dose of the vaccine. Failure to have blood drawn for baseline and/or 4 weeks after vaccination will also warrant replacement.

Subjects will not be replaced if they fail to present to the blood draw 24 months post-vaccination.

In the case of a change of therapy between the first and second dose of the vaccine (including the addition of rituximab), patients will remain on study and will not be replaced. Their data will be included in the estimates of vaccine response in the intent-to-treat analysis but excluded from sub-group analyses.

Based on data from the University of Rochester Cancer Center pharmacy, as of May 2018, 150 CLL and WM patients are on BTK inhibitor therapy and there are approximately 20 new cases per month. A local CLL database confirms those numbers and shows that a total of about 50 patients are on single-agent, first-line ibrutinib as of January 2018. No patient was identified while collecting this data, with respect to patients' confidentiality.

Patients who have started BTK inhibitors come to clinic about every 3 months for routine visits. Based on those numbers, we expect the recruitment of 33 patients to be feasible within 6 months.

b) Gender and Age of Subjects:

Subjects must be at least 50 years old to participate. Patients under 50 years old are excluded as per the label of the vaccine. It is anticipated that most subjects will be in their sixth or seventh decade given the age distribution of CLL²³ and WM.²⁴ There is no upper age limit if the patient meets the other inclusion criteria.

We expect that only a minority of subjects will be diagnosed with WM as compared to CLL because it is a much rarer disease, with only 1400 new cases diagnosed each year in the United States.^{25,26}

All genders are accepted. It is expected that there will be slightly more males than females included in the study as the male-to-female ratio in CLL is normally 1.3-1.7.²⁷ and about 60% of WM patients are males.²⁴

c) Racial and Ethnic Origin:

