These analyses will be repeated 24 months after the last dose of the vaccine to assess long term immunogenicity, at visit 5. A last chart review also be performed to assess incidence of zoster reactivation and disease progression as determined by their team of providers during the latest visit.

Table 1. Schedule of Study Procedures

Visit	Screen*	1*	2	3	4	5
		Dose 1	Safety assessment	Dose 2	Blood draw	Optional Blood draw
Visit window		0	Week 4 ± 1 week	Weeks 8-12	4 Weeks ± 1 week after Dose 2	24 months ± 3 months of Dose 2
Obtain informed consent	X					
Confirm eligibility	X					
Enroll	X					
Vaccine administration	X*	X*		X		
Lab work (anti-gE and CMI)	X*	X*			X	X
Safety assessment (patient-reported AEs)			X		X	

and chart review)						
-------------------	--	--	--	--	--	--

*Note: Administration of the first dose of the vaccine and completion of the lab assays will take place once, either at the screening visit OR at the first visit. If this is done at screening, then screening and visit one will happen within the same visit.

Subjects will be contacted through phone call OR in person at the clinic on for safety assessment.

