5.2. Efficacy Assessments

Vaccine response, as determined by blood antibody levels to the varicella virus glycoprotein E subunit (anti-gE), will be measured by ELISA. This humoral response will be assessed four weeks after vaccination is complete. In patients who were seropositive before the study, a positive response will be defined as at least a four-fold increase in geometric mean concentration (GMC) of anti-VZV gE antibody as measured per ELISA. Humoral response in seronegative patients at baseline will be defined as at least a four-fold increase from the lower detection limit of the anti-gE antibody assay.

Secondary efficacy objectives include:

1. Measure humoral response at 24 months post-vaccination, which is defined as persistence of anti-gE antibody above test threshold at 24 months.
2. Measure cell-mediated response to vaccination at one month and 24 months after vaccination.
3. Evaluation of CLL/WM progression on BTK inhibitor as determined by treating oncologist at latest assessment, and correlation between progression on BTK inhibitor and vaccine response at 4 weeks and at 24 months post-second dose.

Cellular-mediated response will be determined by measuring PBMC activation (by ELISPOT or flow cytometry) following stimulation with varicella glycoprotein E peptide. PBMC activation at 4 weeks and 24 months post dose will be compared to pre-vaccination activation levels.

a. Safety Assessments

Subjects will be educated to recognize immediate adverse reactions to the vaccine. Patient-reported signs of allergic or hypersensitivity reactions will be assessed and managed by the study team as needed. Only severe adverse effects will be captured in this study. Subjects will be contacted 4 weeks \pm 1 week after each dose of the vaccine for assessment and their chart will be reviewed at the same moment. Severe adverse effects are defined as any grades 3-5 adverse effects included in the CTCAE v5.0 classification.

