6. CONCOMITANT AND DISALLOWED MEDICATIONS

Subjects will be required to have been on first-line BTK inhibitors for at least 3 months at study start. Prior dose reductions for toxicity will be allowed.

Subjects will not be asked to discontinue any medication to participate in the study. However, prior use of other medications designed to treat specifically CLL or WM (i.e. venetoclax) will not

be allowed. Change in medication as determined by treating oncologist will be allowed.

Other vaccination will be allowed during the study provided it does not interfere with the study assays. Administration of another inactivated vaccine (for example influenza or pneumococcal vaccine) will only be authorized outside that critical time period that ranges from 7 days prior to the first dose until 7 days post-second dose. We will encourage patients to receive the influenza vaccine and come back for the study protocol 7 days later should this interfere with our study.

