13.2. Planned Statistical Analysis

13.2.a Primary Analysis

The estimates of geometric mean antibody titers pre- and post-vaccination, mean fold-changes, and vaccine response rates will be described with 90% (two-sided) confidence intervals. These estimates will be important for designing a future vaccine trial in patients treated with BTK inhibitors with emergence of shingles as the primary outcome. Self-reported and chart-reviewed serious adverse events will be summarized in tabular format by type and grade.

13.2.b Secondary and Exploratory Analyses

As secondary analyses, the change in antibody titers pre and post-vaccination will be evaluated with the Wilcoxon Rank Signed Test for paired data. This test will provide some indication whether the within subject change in titer is statistically different from zero. The change in seroprotection rates pre and post vaccination will be assessed by the exact McNemar test for paired proportions.

As exploratory analyses, the association between baseline characteristics and the achievement of immunological response and change in antibody titers will be assessed using exact non-parametric statistical tests, such as exact Chi-Square test, Wilcoxon Rank Sum test, or Spearman rank correlation tests, depending on the scale of the variables involved. Baseline characteristics of particular interest have been described above and include age, stage at diagnosis, time since diagnosis, presence of high-risk or low-risk features, time since BTK inhibitor therapy initiation, history of zoster reactivation, IgG levels at study entry and use of rituximab therapy. These results will be reported along with descriptive statistics for the purpose of hypothesis generation in future trials.

The disease progression to BTK inhibitor at visit 4 and visit 5 will be determined from the closest assessment by treating oncologist. The association between vaccine response and disease progression at each time point will be assessed with Fisher's exact test.

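### The response–progression association is not pinned down: read as same-visit tests, Visit 4 will have too few progressions and Visit 5 is limited to attenders, and week-4 response against 24-month progression is never named

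*Combined protocol and SAP*

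**What the plan says.** Correlating progression on the BTK inhibitor with vaccine response at 4 weeks and 24 months is a listed secondary objective (Protocol Summary, sections 1.1 and 5.2). Its analysis is two sentences in section 13.2.b. The first is "The disease progression to BTK inhibitor at visit 4 and visit 5 will be determined from the closest assessment by treating oncologist". The second says that "The association between vaccine response and disease progression at each time point will be assessed", and names Fisher's exact test. Neither gives an alpha level, an analysis set or the definition of response that applies.

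Other sections bear on this:

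- **Timing.** Table 1 (section 5) puts dose 2 at weeks 8–12 and Visit 4 at "4 Weeks ± 1 week after Dose 2". Section 8.4 also keeps patients whose second dose comes as late as 6 months after the first.
- **Visit 5.** Table 1 labels the draw as optional. Section 3.1 adds: "Subjects will not be replaced if they fail to present to the blood draw 24 months post-vaccination".
- **Progression.** Section 5 obtains it by chart review, separately from the draw. Section 5.2 takes it "as determined by treating oncologist at latest assessment", and section 5 likewise uses the latest visit. Section 13.2.b uses the closest assessment.
- **Response.** Section 5.2 defines it at 4 weeks as a four-fold rise, and at 24 months as antibody remaining above the assay threshold.
- **Therapy.** Section 6 states: "Change in medication as determined by treating oncologist will be allowed".

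**The concern.** If response and progression are paired visit by visit, neither test serves the objective well. At Visit 4 hardly anyone will have had time to progress. At Visit 5 response is known only for those who return, and it is measured after any progression and any change of therapy. Patients who progressed may be the ones who do not return, so response could be missing or altered because of progression.

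The study plans to collect what a better comparison needs: response at week 4, before most of the follow-up, and progression to 24 months from the chart. Because the pairing is not stated, it could also be chosen after the data are seen, when a handful of events decides the result.

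**Working it through.** **The plan's own figures.** The documents give no power or sample size for this association. The design numbers they do give reproduce: 30 × 1.10 = 33 enrolled, and all 21 Clopper-Pearson intervals in Table 3 match (for example 70–94% at 85% with n = 30). The study was sized for the precision of the response rate, not for this test.

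**When Visit 4 falls.** Earliest 8 + 3 = 11 weeks after dose 1; latest 12 + 5 = 17 weeks. With dose 2 at 6 months (26 weeks) under section 8.4, 26 + 5 = 31 weeks. Section 3.1 puts routine clinic visits about 3 months apart. The latest assessment before Visit 4 can therefore date from around dose 1, while the closest one may fall after Visit 4. The two rules can select different records.

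**Events expected in 30 patients.** The documents give no progression rate, so constant hazards h of 0.05 and 0.20 per year are assumed. Expected events = 30 × (1 − exp(−h × t)):

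| Time from dose 1 | h = 0.05 | h = 0.20 |
|---|---|---|
| 11 weeks | 0.3 | 1.2 |
| 17 weeks | 0.5 | 1.9 |
| 31 weeks (if all were that late) | 0.9 | 3.4 |
| 24 months | 2.9 | 9.9 |

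**Events needed.** The smallest attainable two-sided Fisher p-value, with all events in one group and alpha of 0.05 assumed:

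- 15/15 split: 1.0, 0.48, 0.22, 0.10 and 0.042 for 1 to 5 events, so at least 5 are needed.
- 12 responders, 18 non-responders: 7 if all are non-responders (p = 0.024), 4 if all are responders (p = 0.018).
- 21/9 split: 3 if all are in the group of nine (p = 0.021).

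If 3% have progressed by Visit 4, the chance of no event in 30 is 0.97^30 = 40%, and the chance of 5 or more is 0.2%.

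**Power, exact Fisher by enumeration, equal split.** The 24-month rates and the figure of 20 usable patients are assumptions:

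| 24-month progression, responders vs non-responders | All 30 | 20 usable |
|---|---|---|
| 5% vs 20% | 8% | 2% |
| 10% vs 30% | 15% | 6% |
| 10% vs 50% | 54% | 30% |

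For 10% vs 50%, scaling each rate p to w weeks as 1 − (1 − p)^(w/104.3) gives 1.4% vs 8.9% at 14 weeks. Visit 4 power is then about 0.6%; it is 1.3% at 17 weeks and about 8.5% if every patient were at 31 weeks.

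**Effect of starting the count at Visit 4.** In the 10% vs 50% case, 15 × (0.014 + 0.089) = 1.5 of the 15 × (0.10 + 0.50) = 9 expected events precede a 14-week Visit 4. Removing those patients leaves rates of (0.10 − 0.014)/0.986 = 8.7% and (0.50 − 0.089)/0.911 = 45%. Averaged over the number still at risk, power is about 52%. The other two rows stay at about 8% and 15%.

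**The case against.** The strongest objection is that the cross-time comparison may already be intended. In 13.2.b the phrase about each time point can attach to progression alone. Section 5.2 introduces vaccine response as the four-week humoral measure and treats 24-month persistence separately. A reader might infer that week-4 response against 24-month progression has been left out of the plan. The documents do not support that: the pairing is unspecified, not ruled out. What remains is that the same-visit reading is the more natural one and nothing in the text settles it.

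A reader might also infer that the Visit 5 pairing is an error because response follows progression. That is too strong. The objective is only to correlate, no section says response should predict progression, and the background describes disease impairing vaccine response. Response in patients who have progressed is a fair question. The limits on the Visit 5 test are selection by attendance and possible therapy change.

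Three further points stand. Section 8.4 means 17 weeks is not a hard upper limit for Visit 4. Progression to 24 months cannot be assumed known for everyone, because section 4.2 asks permission for the later chart review as well as the sample, and section 7 ends data collection once consent is withdrawn. And 10% vs 50% is a large contrast; under milder rates the preferred analysis is weak too.

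That this is a pilot explains low power. It does not explain leaving the pairing and analysis set of a listed objective open.

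**Conclusion.** The concern holds in a limited form. As most naturally read, 13.2.b gives a Visit 4 test that can rarely be informative and a Visit 5 test confined to attenders of an optional draw. The comparison that makes most use of the planned data is not named.

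The gain from naming it is more events (about 3–10 by 24 months against 0.3–1.9 by Visit 4 at the assumed hazards) and more patients, not adequate power. At 15/15, power is about 8%, 15% or 54% for the three assumed contrasts. These figures rest on assumed progression rates, responder split, attendance and a two-sided 0.05 level, none of which the documents give. The Visit 4 conclusion is less secure if many second doses are late or the responder split is very uneven.

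The point affects one secondary objective and leaves the primary endpoint untouched. It should be fixed because the remedy is nearly free and closes off a choice that could otherwise be made after seeing the data.

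**What to change.** In section 13.2.b:

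1. Name the main association analysis: week-4 response (the four-fold definition) against progression after Visit 4 up to 24 months, in all evaluable patients with permitted chart follow-up, by Fisher's exact test. Patients who have already progressed by Visit 4 are counted separately.
2. Record the chart date of progression, so that a time-to-progression display with Visit 4 as landmark can be added.
3. Report progression at Visit 4 as counts, without a test.
4. Keep the same-visit association at Visit 5 as a descriptive analysis of attenders. State which response definition it uses and how many patients lack a sample.
5. Use one rule for selecting the progression assessment, latest or closest, in sections 5, 5.2 and 13.2.b.
6. Say that the analysis is exploratory.

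The cost is a few sentences of SAP text and the abstraction of progression dates during chart reviews already planned. No visit or sample is added.

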1. PURPOSE OF THE STUDY AND BACKGROUND

1.1. Purpose of the study

Chronic lymphocytic leukemia (CLL) and Waldenstrom's macroglobulinemia (WM) are known risk factors for zoster reactivation, commonly called shingles. Although a recently FDA-approved recombinant, adjuvanted herpes zoster vaccine (Shingrix) is currently being offered to these populations, no study has specifically evaluated them in combination with BTK inhibitors.

The purpose of the study is to complete a single-arm trial evaluating if patients with CLL or WM, while on treatment with first-line BTK inhibitors, can achieve immunologic response to Shingrix. If effective, this will result in a new, well-tolerated shingles prevention strategy for these patients.

Primary objective:

- To measure the humoral immune response 4 weeks after the completion of vaccination with the Shingrix vaccine in patients \geq 50 years with CLL and WM receiving first-line treatment with BTK inhibitors.

Secondary objectives include:

- To measure the humoral immune response at 24 months after the completion of vaccination with the Shingrix vaccine in patients \geq 50 years with CLL and WM receiving first-line treatment with BTK inhibitors.
- To measure PBMC activation by ELISPOT and/or flow cytometry at 4 weeks and 24 months following vaccination with Shingrix, as a marker of cellular mediated immunity.
- To determine the rate of lymphoma progression while receiving BTK inhibitors.
- To correlate lymphoma progression while receiving BTK inhibitors and vaccine response at 4 weeks and 24 months following the vaccination.

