13. DATA ANALYSIS AND MONITORING

13.1. Sample Size Determination

The primary endpoint for assessing the immunological response to the vaccine has been defined in section 5.2. The target accrual will be 30 evaluable subjects receiving treatment with BTK inhibitor. Allowing for 10% drop-out due to subject participation or lab testing issues, this trial will accrue a total of 33 CLL or WM patients. Based on current estimates, the expected time to accrue these subjects is 6 months.

We expect that the response to vaccine will be significantly less than the 97% response rate seen in the healthy general population. The table below shows the exact Clopper-Pearson two-sided 90% confidence intervals for a range of likely observed response rates for a range of sample sizes. The upper bound of the 90% (two-sided) confidence interval corresponds to a (one-sided) 95% confidence interval. Therefore, with 30 evaluable subjects and observed response rate

<85%, we will have 95% confidence that the true immunological response rate is less than the general population response rate.

Table 3: Two-sided 90% Confidence Intervals for a range of potential response rates by sample size

Immunologic Response Rate (%)	Sample Size		
	20	25	30
25	10 – 46%	12 – 43%	13 – 41%
35	18 – 56%	19 – 53%	21 – 52%
45	26 – 65%	28 – 63%	29 – 61%
55	35 – 74%	37 – 72%	39 – 71%
65	44 – 82%	47 – 81%	48 – 79%
75	54 – 90%	57 – 88%	59 – 87%
85	66 – 96%	68 – 95%	70 – 94%

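### The secondary objective linking vaccine response to progression rests on a yes/no Fisher test alone; adding an exact comparison of titres would gain power when progressions are few

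*Combined protocol and SAP*

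**What the plan says.** Section 1.1 lists as a secondary objective: "To correlate lymphoma progression while receiving BTK inhibitors and vaccine response at 4 weeks and 24 months following the vaccination". Section 5.2 repeats it as the "correlation between progression on BTK inhibitor and vaccine response at 4 weeks and at 24 months post-second dose". The only analysis assigned to it is in section 13.2.b: "The association between vaccine response and disease progression at each time point will be assessed with Fisher's exact test".

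Section 5.2 makes response binary at both times. At 4 weeks it is a four-fold rise in anti-gE, measured from the assay's lower detection limit in subjects who start seronegative. At 24 months it is "persistence of anti-gE antibody above test threshold at 24 months".

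The same section 13.2.b treats the exploratory baseline characteristics more fully. Their association with "achievement of immunological response and change in antibody titers will be assessed using exact non-parametric statistical tests", and rank-sum and Spearman tests are named as options. The mixed model at the end of 13.2 adjusts for baseline characteristics and does not mention progression.

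On size, section 13.1 says "The target accrual will be 30 evaluable subjects receiving treatment with BTK inhibitor". No progression rate, alpha or power is given for this objective.

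**The concern.** Progressions may be few in about 30 subjects. A 2x2 table with a small margin has only a few possible p-values, and sometimes none is below 0.05. In that case a non-significant result follows from the margins and says nothing about whether response and disease control are related. The trial will hold the titres behind the yes/no classification, and the plan uses them for exploratory questions but not for this secondary objective. The risk is that an uninformative result is taken as evidence that vaccine response and progression are unrelated.

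**Working it through.** **Inputs from the documents.** N = 30 evaluable (13.1); response rates of 25% to 85% (Table 3); binary response (5.2). **Assumed, because not stated:** k = 1 to 9 progressions; two-sided 0.05.

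**The plan's own figures.** All 21 Clopper-Pearson intervals in Table 3 reproduce to the rounded percent (for example 55% at n=30 gives 39–71%). Accrual is 30 × 1.10 = 33.

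**Smallest attainable Fisher p.** With r responders, k progressors and a responders among the progressors, P(a) = C(r,a)·C(30−r,k−a)/C(30,k). The two-sided p sums P over all tables no more probable than the one observed. Example: r=17, k=3, no progressor responding gives C(13,3)/C(30,3) = 286/4060 = 0.070. The opposite extreme has probability 680/4060 = 0.167, so it is not added and p = 0.070.

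The columns for 1 to 4 events give the smallest p in either direction. The last column counts only tables in which progressors respond less often. Half-subjects are rounded up.

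| Response | r | 1 event | 2 | 3 | 4 | First k below 0.05, progressors respond less |
|---|---|---|---|---|---|---|
| 25% | 8 | 0.27 | 0.064 | 0.014 | 0.003 | none to 9 (0.067 at 9) |
| 35% | 11 | 0.37 | 0.126 | 0.041 | 0.012 | 7 (0.029) |
| 45% | 14 | 0.47 | 0.209 | 0.090 | 0.037 | 5 (0.045) |
| 55% | 17 | 0.43 | 0.179 | 0.070 | 0.026 | 4 (0.026) |
| 65% | 20 | 0.33 | 0.103 | 0.030 | 0.008 | 3 (0.030) |
| 75% | 23 | 0.23 | 0.048 | 0.009 | 0.001 | 2 (0.048) |
| 85% | 26 | 0.13 | 0.014 | 0.001 | <0.001 | 2 (0.014) |

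Below 50% response, the small values in the columns for 1 to 4 events come from tables in which the progressors are the responders. In the other direction, 10 of 30 responders gives p = 0.53, 0.27, 0.14, 0.074 and 0.064 for 3 to 7 events, and 0.029 at 8. At exactly 15 of 30, which is not a Table 3 row, 4 events still give 0.100 and 5 give 0.042.

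**Sensitivity to alpha.** At two-sided 0.10, 3 events suffice at every Table 3 rate. Two events still fail at 35–65%, and one event fails throughout.

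**The 24-month time point.** Section 3.1 does not replace subjects who miss that draw, so N may be lower. At N=20, 2 events reach 0.05 only at 85% response (0.016; it is 0.053 at 75%).

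**Rank-sum on titres.** Without ties the smallest two-sided p is 2/C(30,k): 2/30 = 0.067 for one event, 2/435 = 0.0046 for two and 2/4060 = 0.0005 for three.

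**Simulated power** (N=30, two-sided 0.05, normal log fold rise 1 SD lower in progressors, no ties, response rate as in non-progressors):

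| Response | Events | Fisher | Exact rank-sum |
|---|---|---|---|
| 40% | 3 | under 1% | about 30% |
| 40% | 5 | about 4% | about 46% |
| 60% | 3 | about 7% | about 28% |
| 60% | 5 | about 29% | about 47% |

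Repeat runs agree within about three percentage points.

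**Effect of ties.** If 15 of 30 values tie at a floor and every progressor is among them, the smallest exact rank-sum p is 0.37, 0.17 and 0.08 for 2, 3 and 4 events. With half of non-progressor values at the floor and 40% response, power is about 0.5% at 3 events and 12.5% at 5. It stays no lower than Fisher's, but at 3 events the gain is essentially gone.

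**The case against.** The best defence is that Fisher's test matches the protocol's own definition of response, which is binary, and that this is a pilot whose primary analysis is estimation. The documents set no alpha, no power and no event count here, and do not say how a non-significant result would be read. The first part stands: the Fisher test answers the objective as worded and should stay.

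A reader might infer that Fisher cannot reach 0.05 at most plausible event counts, so that a null result is close to guaranteed. The documents do not support this. They give no progression rate, and over 8 to 20 responders and 2 to 9 events some table reaches 0.05 in 83 of 104 combinations (55 of 104 if progressors must respond less often). The 15-of-30 case is the least favourable margin. At 75% and 85% response, two events are enough.

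The alternative also has limits. The rank-sum test cannot reach 0.05 with one event, its power is modest with few events, and ties at the detection limit erode it. Fold rise also does not correspond to the 24-month definition. These limits shape the fix. They do not explain why titres are used for exploratory associations and left out of this secondary one.

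**Conclusion.** The concern holds in a limited form. Fisher's test on yes/no response is the only analysis named for this secondary objective. With about 3 or fewer progressions it has little or no attainable significance over much of Table 3's range. If progressors respond less often, that extends to more events at low response rates. It is not a test that must fail: from 4 events, 0.05 is attainable at every Table 3 rate in at least one direction. A titre comparison would be more sensitive, by roughly 18 to 42 percentage points in the four settings simulated.

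The size rests on assumptions the documents do not supply: 1 to 9 events, two-sided 0.05, a 1 SD shift and no ties. Whether the shortfall matters in practice depends mainly on how many subjects progress.

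**What to change.** In section 13.2.b, keep the Fisher test and the 2x2 table at each time point. Add an exact permutation Wilcoxon rank-sum comparison, corrected for ties, between progressors and non-progressors. Use log fold rise in anti-gE at 4 weeks and log anti-gE titre at 24 months. Report a Hodges-Lehmann ratio with a 90% interval, the level the plan uses for its primary estimates. State the number of progressions at each visit and the number of values at the assay's lower limit, and say that a non-significant result will not be read as no association.

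The cost is a few sentences of wording and one additional secondary test. No new samples or subjects are needed, and the rank-sum test is already named in the section. The addition will not rescue the objective if only one subject progresses.
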